13. ADVERSE EVENTS

13.1. Definitions and Classifications

Adverse Event (AE) – An AE is “any untoward medical occurrence, unintended disease or injury, or untoward clinical signs (including abnormal laboratory findings) in subjects, users or other persons, whether or not related to the investigational medical device.

Note 1 to entry: This definition includes events related to the investigational medical device or the comparator.

Note 2 to entry: This definition includes events related to the procedures involved.

Note 3 to entry: For users or other persons, this definition is restricted to events related to investigational medical devices.”¹

An AE includes any condition (including a pre-existing condition) that:

1. Was not present prior to the study, but appeared or reappeared following initiation of the study
2. Was present prior to the study but worsened during the study. This would include any condition resulting from concomitant illnesses, reactions to concomitant medications, or progression of disease states
3. Pregnancy must be documented as an adverse event and must be reported to the clinical monitor and to the Sponsor immediately upon learning of the event

Serious Adverse Event (SAE) – An SAE is any untoward medical occurrence that:

- Results in death
- Is life threatening
- Requires in-patient hospitalization or prolongation of existing hospitalization
- Results in persistent or significant disability/incapacity (e.g., a sight threatening event, a significant persistent or permanent change, impairment, damage, or disruption to the subject’s body)
- Is a congenital anomaly/birth defect
- Requires intervention to prevent permanent damage (the use of the test article resulting in a condition which requires medical or surgical intervention to preclude permanent impairment of the body structure or a body function). Important medical events that may not result in death, be life-threatening, or require hospitalization may be considered an SAE when, based upon appropriate medical judgment, they may jeopardize the patient or subject and may require medical or surgical intervention to prevent one of the outcomes listed in the above definition

Diagnoses and conditions that are considered Ocular Serious Adverse Events include, but not limited to:

- Microbial Keratitis (MK)
- Iritis (including cells in the anterior chamber)
- Permanent decrease in best spectacle corrected visual acuity equivalent to 2 acuity lines or greater
- Central Corneal Opacity
- Central Corneal Neovascularization
- Uveitis
- Endophthalmitis
- Hypopyon
- Hyphemia
- Penetration of Bowman’s Membrane

- Persistent Epithelial Defect
- Limbal cell Damage leading to Conjunctivalization

Significant Adverse Events – Those events that are usually symptomatic and warrant discontinuation (temporary or permanent) of the test article (excluding Serious Adverse Events).

Diagnoses and conditions that are considered Ocular Significant Adverse Events include, but not limited to the following:

- Contact Lens Induced Peripheral Ulcer (CLPU)
- Significant Infiltrative Events (SIE)
- Superior Epithelial Arcuate Lesions (SEALs)
- Any Temporary Loss of > 2 Lines of BSCVA
- Other Grade 3 or higher corneal findings, such as abrasions or edema
- Non-contact lens related corneal events - e.g. Epidemic Keratoconjunctivitis (EKC)
- Asymptomatic Corneal Scar
- Any corneal event which necessitates temporary lens discontinuation > 2 weeks

Non-Significant Adverse Events – Those conditions that are usually asymptomatic and usually do not warrant discontinuation (temporary or permanent) of the test article. However, the Investigator may choose to treat as a precautionary measure.

Diagnoses and conditions that are considered Ocular Non-Significant Adverse Events include, but not limited to the following:

- Non-significant Infiltrative Event (NSIE)
- Contact Lens Papillary Conjunctivitis (CLPC)
- Superficial Punctate Keratitis (SPK)
- Conjunctivitis: Bacterial, Viral, Allergic
- Blepharitis
- Meibomianitis
- Contact Dermatitis
- Localized Allergic Reactions
- Any corneal event not explicitly defined as serious or significant adverse event, which necessitates temporary lens discontinuation < 2 weeks

Adverse Device Effect (ADE) – An ADE is an “adverse event related to the use of an investigational medical device.

Note 1 to entry: This definition includes adverse events resulting from insufficient or inadequate instructions for use, deployment, implantation, installation, or operation, or any malfunction of the investigational medical device.

Note 2 to entry: This definition includes any event resulting from use error or from intentional misuse of the investigational medical device.”¹

Unanticipated Adverse Device Effect (UADE) – Any serious adverse effect on health or safety or any life-threatening problem or death caused by, or associated with, the test article,

if that effect, problem, or death was not previously identified in nature, severity, or degree of incidence in the investigational plan, Investigator's Brochure or protocol, or any other unanticipated serious problem associated with the test article that relates to the rights, safety and welfare of subjects.

13.2. Assessing Adverse Events

In conjunction with the medical monitor, the Investigator will evaluate adverse events to ensure the events are categorized correctly. Elements of categorization will include:

- Seriousness/Classifications (see definition in Section 13.1)
- Causality or Relatedness – i.e. the relationship between the test article, study treatment or study procedures and the adverse event (not related; unlikely related; possibly related; related - see definition in Section 13.2.1)
- Adverse Event Severity – Adverse event severity is used to assess the degree of intensity of the adverse event (mild; moderate; severe for all events - see definition in Section 0)
- Outcome – not recovered or not resolved; recovering or resolving; recovered or resolved with sequelae; recovered or resolved; death related to adverse event; unknown
- Actions Taken – none; temporarily discontinued; permanently discontinued; other

13.2.1. Causality Assessment

Causality Assessment – A determination of the relationship between an adverse event and the test article. The test article relationship for each adverse event should be determined by the investigator using these explanations:

- Not Related- An adverse event that is not related to the use of the test article, study treatment or study procedures
- Unlikely Related – An adverse event for which an alternative explanation is more likely, e.g. concomitant treatment, concomitant disease(s), or the relationship of time suggests that a causal relationship is not likely
- Possibly Related – An adverse event that might be due to the use of the test article, or to the study treatment or study procedures. An alternative explanation, e.g. concomitant treatment, concomitant disease(s), is inconclusive. The relationship in time is reasonable. Therefore, the causal relationship cannot be excluded
- Related – An adverse event that is listed as a possible adverse effect (device) or adverse reaction (drug) and cannot be reasonably explained by an alternative explanation, e.g. concomitant treatment of concomitant disease(s). The relationship in time is very suggestive, e.g. it is confirmed by de-challenge and re-challenge

13.2.2. Severity Assessment

Severity Assessment – A qualitative assessment of the degree of intensity of an adverse event as determined by the Investigator or reported to him/her by the subject. The assessment of severity is made irrespective of test article, study treatment or study procedure relationship or seriousness of the event and should be evaluated according to the following scale:

- Mild – Event is noticeable to the subject, but is easily tolerated and does not interfere with the subject’s daily activities
- Moderate – Event is bothersome, possible requiring additional therapy, and may interfere with the subject’s daily activities
- Severe – Event is intolerable, necessitates additional therapy or alteration of therapy and interferes with the subject’s daily activities

13.3. Documentation and Follow-Up of Adverse Events

The recording and documenting of adverse events (ocular and non-ocular) begins when the subjects are exposed to the test article, study treatment or study procedure. Adverse events reported before the use of test article, start of study treatment, or study procedures will be recorded as medical history. However, if the condition deteriorates at any time during the study it will be recorded and reported as an AE. Untoward medical events reported after the subject’s exit from the study will be recorded as adverse events at the discretion of the Investigator.

Upon finding an adverse event, the Principal Investigator will document the condition in the subject record and in the eCRFs. He/she will complete the Adverse Event /eCRF.

Complete descriptions of all adverse events must be available in the subject record. All Adverse Events including local and systemic reactions not meeting the criteria for “serious adverse events” shall be captured on the appropriate case report form or electronic data system. All adverse events occurring while the subject is enrolled in the study must be documented appropriately regardless of relationship.

It is the Investigator’s responsibility to maintain documentation of each reported adverse event. All adverse events will be followed in accordance with applicable licensing requirements. Such documentation will include the following:

- Adverse event (diagnosis not symptom)
- Drawings or photographs (where appropriate) that detail the finding (e.g., size, location, and depth, etc.)
- Date the clinical site was notified
- Date and time of onset
- Date and time of resolution
- Adverse event classification, severity, and relationship to test articles, as applicable
- Treatment regimen instituted, including concomitant medications prescribed, in accordance with applicable licensing requirements
- Any referral to another health care provider if needed
- Outcome, ocular damage (if any)
- Likely etiology
- Best corrected visual acuity at the discovery of the event and upon conclusion of the event

In addition, if an infiltrate(s) is present, he/she will complete the Corneal Infiltrate Assessment eCRF. Where necessary, a culture of the corneal lesion will be collected to

determine if the infection is microbial in nature. If cultures are collected, the date of culture collection and laboratory utilized will be recorded.

Changes in the severity of an AE shall be documented to allow an assessment of the duration of the event at each level of intensity to be performed. Adverse events characterized as intermittent require documentation of the onset and duration of each episode. Changes in the assessment of relationship to the test article shall also be clearly documented.

Subjects who present with an adverse event shall be followed by the Investigator, within licensure, until all signs and symptoms have returned to pre-treatment status, stabilized, or been satisfactorily resolved. If further treatment beyond licensure is required, the patient will be referred to the appropriate health care provider. The Investigator will use his/her clinical judgment as to whether a subject reporting with an adverse event will continue in the study. If a subject is discontinued from the study, it will be the responsibility of the Investigator to record the reason for discontinuation. The Investigator will also document the adverse event appropriately and complete the Adverse Event eCRF. Any subjects with ongoing adverse events related to the test article, study treatment or study procedures, as of the final study visit date, should be followed to resolution of the adverse event or until referral to an appropriate health care provider, as recommended by the Investigator. Non-ocular adverse events that are not related to the test article, study treatment, or study procedures may be recorded as "ongoing" without further follow-up.

13.4. Reporting Adverse Events

The Investigator will notify the Sponsor of an adverse event by e-mail, facsimile, or telephone as soon as possible and no later than 24 hours from discovery for any serious /significant adverse events, and 2 days from discovery for any non-significant adverse event. In addition, a written report will be submitted by the Principal Investigator to the IEC/IRB according to their requirements (Section 13.4.2). The report will comment whether the adverse event was considered to be related to the test article, study treatment or study procedures.

13.4.1. Reporting Adverse Events to Sponsor

Serious/Significant Adverse Events

The Investigator will inform the sponsor of all serious/significant adverse events occurring during the study period as soon as possible by e-mail, fax, or telephone, but no later than 24 hours following discovery of the event. The Investigator is obligated to pursue and obtain information requested by the Sponsor in addition to that information reported on the eCRF. All subjects experiencing a serious/significant adverse event must be followed up and all outcomes must be reported.

When medically necessary, the Investigator may break the randomization code to determine the identity of the treatment that the subject received. The Sponsor and study monitor should be notified prior to unmasking the test articles.

In the event of a serious/significant adverse event, the Investigator must:

- Notify the Sponsor immediately

- Obtain and maintain in the subject's records all pertinent medical information and medical judgment for colleagues who assisted in the treatment and follow-up of the subject
- Provide the Sponsor with a complete case history which includes a statement as to whether the event was or was not related to the use of the test article
- Notify the IEC/IRB as required by the IEC/IRB reporting procedure according to national regulations

Unanticipated (Serious) Adverse Device Effect (UADE)

In the event of an Unanticipated (Serious) Adverse Device Effect (UADE), the Investigator will submit a report of the UADE to the Sponsor and IEC/IRB as soon as possible, but no later than 24 hours after the Investigator first learns of the effect. This report is in addition to the immediate notification mentioned above.

The Sponsor must conduct an evaluation of the UADE and must report the results of the evaluation to FDA, the IEC/IRB and participating Investigators within 10 working days after the Sponsor first receives notification of the effect.

Non-Serious Adverse Events

All non-serious adverse events, including non-serious adverse device effects, will be reported to the sponsor by the Investigator no later than 2 days from discovery.

13.4.2. Reporting Adverse Events to the Responsible IEC/IRB and Health Authorities

Adverse events that meet the IEC/IRB requirements for reporting must be reported within the IEC/IRB's written guidelines. Each clinical site will refer to and follow any guidelines set forth by their Approving IEC/IRB. Each clinical site will refer to and follow any guidelines set forth by their local governing Health Authorities.

The Sponsor will report applicable Adverse Events to the local health authorities according the written guidelines, including reporting timelines.

13.4.3. Event of Special Interest

None

13.5. Reporting of Pregnancy

Subjects reporting pregnancy (by self-report) during the study will be discontinued after the event is recorded as an Adverse Event. Once discontinued, pregnant participants and their fetuses will not be monitored for study related purposes. At the Investigator's discretion, the study participant may be followed by the Investigator through delivery. However, this data will not be collected as part of the clinical study database. Pregnant participants are not discontinued from contact lens or solution related studies for safety concerns, but due to general concerns relating to pregnancy and contact lens use. Specifically, pregnant women are discontinued due to fluctuations in refractive error and/or visual acuity that occur secondary to systemic hormonal changes, and not due to unforeseen health risks to the mother or fetus.

14. STATISTICAL METHODS

14.1. General Considerations

All data summaries and statistical analyses will be performed using the Statistical Analysis System (SAS) software Version 9.4 (SAS Institute, Cary, NC). Throughout the analysis of data, the results for each subject/eye will be used when available for summarization and statistical analysis. Unscheduled visits will be summarized separately and will be excluded from the statistical analysis.

Summary tables (Descriptive statistics and/or frequency tables) will be provided for all baseline variables, efficacy variables and safety variables as appropriate. Continuous variables will be summarized with descriptive statistics (n, mean, standard deviation [SD], median, minimum and maximum). Frequency count and percentage of subjects or eyes within each category will be provided for categorical data.

Summaries will be presented by study lens type and will be performed separately by completion status (Safety Population or Per-Protocol Population). All analyses will be conducted on per-protocol population (see Section 14.3).

14.2. Sample Size Justification

Historical study [REDACTED] tested hyperopes in presbyopic population. The data from [REDACTED] was used to estimate the sample size of the study. The rationale is the Test lens in [REDACTED] has the same optical and mechanical designs, but a different curing method compared with both test article in this trial.

Using the POWER procedure in SAS 9.4, the table below shows the power to test the primary hypothesis with overall type I error 0.05 and 50 subjects.

Primary Hypothesis:	Criteria	True Difference (Test-Control)	Power
CLUE Vision	Test-Control>=-5	0	0.48
		2	0.72
		4	0.89

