2.3. Hypotheses

The following primary hypothesis will be tested throughout this investigation.

Primary Hypothesis:

1. After 14 to 20 days of wear, the PRO CLUE vision scores for the Test lens will be non-inferior to the Control lens. A non-inferiority margin of 5 CLUE points will be used. This will be recorded by the subject using the CLUE Follow-up Questionnaire.

If the primary hypothesis is met, the following secondary hypotheses will be tested.

Secondary Hypotheses:

1. After 14 to 20 days of wear, the distance, binocular, high luminance, high contrast visual acuity score for the Test lens will be non-inferior to the Control lens. A non-inferiority margin of -0.05 logMAR will be used.
2. After 14 to 20 days of wear, the intermediate, binocular, high luminance, high contrast visual acuity score for the Test lens will be non-inferior to the Control lens. A non-inferiority margin of -0.05 logMAR will be used.
3. After 14 to 20 days of wear, the near, binocular, high luminance, high contrast visual acuity score for the Test lens will be non-inferior to the Control lens. A non-inferiority margin of -0.05 logMAR will be used.

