4.3. Enrollment Target and Study Duration

A total of approximately 60 eligible subjects will be enrolled with 50 targeted to complete the study. The study will last approximately 2-4 months.

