5. TEST ARTICLE ALLOCATION AND MASKING

5.1. Test Article Allocation

The study lenses will be worn in a bilateral and random fashion using a 2×2 crossover design with 2 lens types and 2 periods. Using a computer-generated randomization scheme provided by the study biostatistician, each subject will randomly be assigned to one of two unique sequences (Test/Control or Control/Test). Randomization will be stratified by site.

Permuted block randomization will be used to avoid bias in the assignment of subjects to treatment, and to enhance the validity of statistical comparisons across treatment groups. Each block will contain two different lens trial sequences.

The order of lens wear will be based on the randomization scheme assigned to the study site. The study site will follow the randomization scheme provided and will complete enrollment according to the randomization list and will not pre-select or assign subjects.

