14.4. Level of Statistical Significance

All planned analysis for this study will be conducted with an overall type I error rate of 5%.

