14.5. Primary Analysis

Primary efficacy analysis:

Overall quality of vision scores will be analyzed using a linear mixed model adjusting for baseline values as fixed covariates. The model will include the experimental design factors: sequence of lens wear, period, lens type, time point and interaction between lens and time point as fixed effects. The covariance between residual errors from the same subject across lens wearing periods/time point will be selected based on the finite-sample corrected Akaike's Information Criterion.⁶ Covariance structures considered may include: Homogenous compound symmetry (CS) and Unstructured covariance structure (UN). The structure that returns the lowest Akaike Information Criteria Corrected (AICC) will be selected as the structure that best fit the data.

Comparisons between the Test lens and Control lens at 2-week follow-up will be carried out using 95% confidence intervals constructed of least-square means (LSM) differences (Test minus Control) from the linear mixed model. The non-inferiority of the Test lens relative to the Control will be concluded if the lower confidence limit of LSM difference is above the non-inferiority margin -5. The superiority will be established if the lower confidence limit is above 0.

In all models, the Kenward and Roger method⁷ will be used for the calculation of the denominator of degrees of freedom.

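### The Section 14.2 powers (0.48/0.72/0.89) were computed at one-sided 5%, but the 95% interval rule in Section 14.5 is a one-sided 2.5% test with power of about 0.35/0.60/0.81

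*Combined protocol and SAP*

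**What the plan says.** Section 14.2 (Sample Size Justification) states that "the table below shows the power to test the primary hypothesis with overall type I error 0.05 and 50 subjects". For the criterion that Test minus Control is at least -5, it lists powers of 0.48, 0.72 and 0.89 at true differences of 0, 2 and 4. The SD comes from a redacted historical study and is not printed. Sidedness is not mentioned.

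Section 14.4 is equally silent on sidedness: "All planned analysis for this study will be conducted with an overall type I error rate of 5" per cent.

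Section 14.5 (Primary Analysis) sets the decision rule. The lens comparison at the 2-week follow-up "will be carried out using 95% confidence intervals constructed of least-square means (LSM) differences", and non-inferiority "will be concluded if the lower confidence limit of LSM difference is above the non-inferiority margin -5". The same interval is used to claim superiority if its lower limit is above 0.

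The margin is in Section 2.3: "A non-inferiority margin of 5 CLUE points will be used". The design is a two-period, two-sequence crossover (Section 5.1) with 50 subjects targeted to complete (Section 4.3). Neither a 90% interval nor a one-sided confidence bound is mentioned anywhere.

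**The concern.** An alpha of 5% without sidedness can mean two different tests. Requiring the lower limit of an ordinary 95% interval to clear the margin is a one-sided test at 2.5%. If the power table was computed at one-sided 5%, it describes an easier test than the one that will be run, and every power in it is too high.

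The table is the plan's only justification for 50 subjects. The trial compares one lens design made by two slightly different processes, so a true difference of 0 is the natural planning case, and that row already has the lowest power. Section 2.3 tests the three visual acuity hypotheses only if the primary hypothesis is met, so an overstated primary power carries through to all of them. A reader relying on the table would also misjudge how much a failed non-inferiority result says about the lenses.

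**Working it through.** **Inputs.** Margin 5 (Section 2.3); 50 subjects in a 2×2 crossover (Sections 4.3, 5.1 and 14.2); powers 0.48, 0.72 and 0.89 at true differences d = 0, 2 and 4 (Section 14.2). The SD is not given, so the standard error (SE) of the difference has to be solved for.

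**Formula.** Under the normal approximation, power = Φ((5 + d)/SE − c), where c is the one-sided critical value. There are three equations and two unknowns, SE and c.

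**Step 1: recover the alpha without assuming an SD.** The probits of 0.48, 0.72 and 0.89 are -0.050, 0.583 and 1.227. They should be linear in d with slope 1/SE.
- Least-squares slope: (1.227 + 0.050)/4 = 0.319, so SE ≈ 3.13.
- Extrapolated to d = -5, the fitted line gives -1.648, so c = 1.648 and one-sided alpha = 0.0497.

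The powers are rounded to two decimals. Allowing ±0.005 on each, the compatible alphas run from about 0.044 to 0.056. This range includes 0.05 and excludes 0.025.

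**Step 2: reproduce the table at one-sided 5%.** With SE = 3.138 and c = 1.645:
- d = 0: 5/3.138 − 1.645 = -0.052, power 0.479
- d = 2: 7/3.138 − 1.645 = 0.586, power 0.721
- d = 4: 9/3.138 − 1.645 = 1.223, power 0.889

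All three match the plan. The noncentral t with 48 df gives the same powers at SE = 3.094, which corresponds to an SD of paired differences of 3.094 × √50 ≈ 21.9.

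**Step 3: try one-sided 2.5%.** These are the SE ranges compatible with each stated power (±0.005, noncentral t, 48 df):

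| Stated power | SE range, one-sided 5% | SE range, one-sided 2.5% |
|---|---|---|
| 0.48 | 3.067–3.116 | 2.549–2.583 |
| 0.72 | 3.077–3.118 | 2.682–2.713 |
| 0.89 | 3.061–3.118 | 2.744–2.790 |

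At 5% the ranges overlap (3.077–3.116). At 2.5% they are disjoint, so no SD yields the table under the Section 14.5 rule. For example, fixing 0.48 at d = 0 forces 0.762 and 0.930 at d = 2 and 4. Using 49 df does not change this. An equivalence test is also ruled out, because its power would fall as d moves from 0 to 4.

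**Step 4: apply the Section 14.5 rule with the same planning SE.**

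| True difference | Stated | Noncentral t, SE 3.094 | Normal, SE 3.138 | t range over SE 3.077–3.116 |
|---|---|---|---|---|
| 0 | 0.48 | 0.353 | 0.357 | 0.349–0.357 |
| 2 | 0.72 | 0.602 | 0.607 | 0.595–0.606 |
| 4 | 0.89 | 0.813 | 0.818 | 0.808–0.818 |

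**Step 5: what the rule demands.** The expected 95% half-width is 2.011 × 3.09 = 6.21 CLUE points, against a margin of 5. The observed Test minus Control must therefore be at least about -5 + 6.21 = +1.2 for non-inferiority to be concluded.

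**The case against.** The arithmetic is not in dispute. The strongest objection is that the plan never says two-sided. If the 95% limit in Section 14.5 is a one-sided bound, Sections 14.2, 14.4 and 14.5 agree and the table is right. That reading is possible but not the ordinary one: the section speaks of confidence intervals and nowhere of a one-sided bound. If a bound was meant, the text has to say so.

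Three further points stand as qualifications:
- **Back-solved SE.** The revised powers re-evaluate the plan's own assumption at 2.5%. The primary model adjusts for baseline and selects its covariance structure from the data, so the achieved SE may differ. The mismatch between table and rule does not depend on the SE.
- **Low power from the start.** At one-sided 5% the half-width would be 1.677 × 3.09 = 5.18, also above the margin, and the printed 0.48 already makes failure slightly more likely than not with identical lenses. The alpha mismatch accounts only for the further 8 to 13 points.
- **Conservative direction.** A one-sided 2.5% test stays within the 5% of Section 14.4, so the false-positive rate is not inflated. The error lies in the stated power.

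**Conclusion.** The concern holds. The powers in Section 14.2 belong to a one-sided 5% test, while Section 14.5, read in the ordinary way, applies a one-sided 2.5% test. Under that rule power is about 0.35, 0.60 and 0.81 at true differences of 0, 2 and 4, instead of 0.48, 0.72 and 0.89. In the most relevant case, no true difference, about two trials in three would fail to show non-inferiority.

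This rests on two assumptions: that the 95% interval is two-sided, and that one planning SE underlies all three rows. The second is supported by the close fit at one-sided 5%.

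**What to change.** **Preferred:** keep the rule in Section 14.5 and correct Section 14.2. State the SD taken from the historical study and that the test is one-sided 2.5%, and recompute the three powers from that SD; they should come out near 0.35, 0.60 and 0.81. Add that the expected 95% half-width, about 6.2 points, exceeds the 5-point margin. The cost is a sentence or two and three less favourable numbers.

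**Alternative:** if one-sided 5% was intended, say so in Section 14.4 and change Section 14.5 to the lower limit of a two-sided 90% interval. The printed powers then stand, but the SD should still be given. This is not a neutral edit: it doubles the one-sided error of the primary test from 2.5% to 5% and, at the planning SE, lowers the observed difference needed from about +1.2 to about +0.2 (-5 + 5.18). It therefore needs a stated rationale and must be settled before unmasking.

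Neither option calls for more subjects.
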